All other SAEs will be reported to the Sponsor and FDA in the Annual Progress Report.

Deaths that are related to research will be reported to the Sponsor immediately upon Investigator notification. A death due to a terminal condition of the research subject would be considered anticipated and not related to the research.

THE SPONSOR WILL REPORT DEATHS TO FDA IN ACCORDANCE WITH 21 CFR 312.

Monitoring

The PI will have the overall responsibility for assuring safety and gathering the data for the study with assistance from the sub-investigators, and research staff, under the guidance of the Institutional Review Board (IRB) and the study Sponsor. Clinical site monitoring will be conducted on behalf of the Sponsor, UAMS, by the Office of Research Regulatory Affairs (ORRA), to ensure that the rights and well-being of human subjects are protected; the trial data are accurate, complete and verifiable from source documents; and the trial is conducted in compliance with currently approved protocol/amendment(s), ICH GCP, and applicable regulatory requirements.

Monitoring specialists from ORRA will conduct periodic on-site, comprehensive monitoring as determined by a protocol-specific monitoring plan, as provided by the ORRA Monitoring Unit.

Study Discontinuation

The Medical Monitor will review **ALL** Grade 3 or higher AEs, using the NCI CTCAE v5.0. Grade 3 AEs are severe or medically significant events (but not immediately life-threatening), hospitalization, or prolongation of hospitalization. The Medical Monitor may choose to halt the study temporarily if serious concerns arise regarding subject safety.

Individual Subject Stopping Rules

Any subject who experiences a grade 3 or higher related AE will discontinue study treatment. The study will be suspended if any subject experiences grade IV or higher related AE. These activities can re-start only after notifying the applicable regulatory authorities and with a permission to resume from the Medical Monitor and Sponsor.

Study Stopping Rules

After accrual of the first six subjects who have been randomly assigned to the Intrarosa® arm, enrollment will be paused until the Medical Monitor has reviewed all Grade 3 or higher AEs in this cohort. The Medical Monitor may begin reviewing the AEs as soon as enrollment is paused; however, review of AEs will continue until each subject in the cohort has either completed study treatment or has otherwise stopped study treatment (see Subject Withdrawal and Subject Termination sections below). If two or fewer subjects (total, regardless of assigned treatment arm) experience a Grade 3 or higher related AE, the study will reopen to enrollment until six more subjects have been randomly assigned to the Intrarosa® arm. Enrollment will once again be paused until the Medical Monitor has reviewed all Grade 3 or higher AEs and approves additional enrollment. Enrollment will continue in cohorts in this manner until either all 60 subjects have been accrued or the study is terminated. If at any point in the study, three or more subjects (cumulative, including both arms) experience Grade 3 or higher related AEs, the study will be terminated.

If the study is prematurely terminated or suspended, the Principal Investigator (PI) will promptly inform study subjects, the IRB, and Sponsor and will provide the reason(s) for the termination or

IRB 239531 Sponsor: UAMS Version 15 0/7/07/2023 Page 16 of 22

suspension. Study subjects will be contacted, as applicable, and be informed of changes to study visit schedule. If only suspended the study may resume once all concerns have been addressed, and satisfy the Sponsor, IRB, and/or the FDA.

Protocol Deviations and Violations

Deviations

Protocol Deviation: any unintentional change, divergence, or departure from the study design or procedures defined in the protocol. Protocol deviations will be tracked and compiled in a Protocol Deviation Log. Deviations should be reported to the IRB at the time of Continuing Review and at the time of the Annual Progress Report (APR). Deviations that potentially cause concern for the subject health, safety, or rights will be reported to ORRA, the Sponsor, as soon as possible for guidance on reporting. Deviations will be made available for Monitors to check against source data at each monitoring visit.

Violations

Protocol violation: a change to, or non-compliance with the IRB-approved procedures without prior Sponsor and IRB approval. Violation may affect health, safety, or rights of a subject. Any violation will be reported immediately to the Sponsor for guidance on reporting. Violations will be made available for Monitors to check against source data at each monitoring visit.

If the protocol deviation/protocol violation does not represent a significant alteration in the approved protocol and/or affect the safety or welfare of the subject, it will be reported to the UAMS IRB at the time of Continuing Review. If the protocol deviation or protocol violation represents a significant alteration in the approved protocol and/or if it affects the safety or welfare of the subject, it must be reported to the UAMS IRB immediately.

Compliance

All drug boxes and unused product will be collected from subject at last visit by research staff and will be given to the research pharmacy to log for compliance. No serious harm is anticipated from non-adherence or cessation of use of the investigational products.

Subject Withdrawal

Subjects may withdraw from treatment or consent from the study at any time for any reason, without penalty.

Subjects who voluntarily withdraw from study treatment will stop taking the study drug but will still participate in the research-related assessments. These research-related assessments include physical exam (including clinical breast and gynecological exam for pH and VMI), estradiol level, completion of BSSC-W, QOL-CSV, and FSFI, and reporting of AEs until the end of the study duration [i.e., Week 12 (±1 week)].

Subjects who withdraw consent from the study will stop taking the study drug and all research-related assessments will be ceased. Any data previously collected will be used but no further data will be collected following the subject's withdrawal of consent. Subjects will be encouraged to report AEs thought to be possibly/probably related to the study drug for 30 days after discontinuation.

For evaluation and reporting purposes, reasons for early withdrawal may be discussed with willing subjects for purposes of identifying potential problems with the drug or study design. When possible, subjects will be notified that any improvement in symptoms they perceived to be the

IRB 239531 Sponsor: UAMS Version 15 0/7/07/2023 Page 17 of 22

result of the study intervention may recede and a return to the pre-study baseline can be expected.

Subject Termination

An investigator may terminate a subject's participation from the study drug treatment to protect the subject from excessive risk without demonstrated benefit (e.g., a side effect such an allergic response making symptoms worsen instead of improve).

Additionally, in the interest of protecting the integrity of the data, an investigator may terminate a subject's participation from the study all together if the subject is not following procedures or is deliberately falsifying information. In the event of termination, the investigator will explain the reasons to the subject and discuss other available treatment options. The subject will refrain from using the study drug and return unused product and packaging for drug accountability. The subject will be instructed to return the completed diary and refrain from using the study drug for 30 days after discontinuation. The subject will also be instructed to report any AEs that occur during the 30 days following drug discontinuation via phone or email to the clinical research nurse. Subjects will be contacted 30 days (+3 days) from the date of drug discontinuation by the clinical research nurse for final safety evaluation. The subject's study status will be listed as 'Withdrawn' and the date of withdrawal will be 30 days (+3 days) after discontinuation. Subjects may obtain drug (Intrarosa® or Replens™) and resume use at their own discretion after the 30-day time period has elapsed after discontinuation.

Specimen Handling and Storage

Vaginal smears will be obtained by scraping the second third of the sidewall of the vagina. A 100-cell count will be performed to classify cells as S, I, and P. Vaginal pH will be measured using a pH indicator strip directly applied to the lateral wall of the vagina. The swab of the vaginal mucosa will be collected during the gynecologic exam, labeled and placed in sterile solution, sent for determination of VMI, then discarded per the usual cytology lab protocol.

Data Analysis

Efficacy and Safety Populations

The efficacy population will include all subjects with a baseline assessment who have received at least two weeks of treatment with either Intrarosa® or Replens™. Subjects who discontinue participation in the study (stop the assigned treatment, withdraw consent, etc.) before 2 weeks of treatment will not be included in the efficacy population. Subjects who discontinue participation in the study after 2 weeks but prior to 12 weeks will be included in the efficacy analysis. These subjects will be invited to complete the end of study evaluation at the time of discontinuation; these evaluation values will be included in the efficacy analyses.

The safety population will include all subjects who received at least one administration of either Intrarosa® or Replens™.

Efficacy Endpoints

The primary efficacy endpoint is VMI Response, which is defined as the change in the subject's calculated VMI from baseline to the end of treatment at 12 (±1 week).

Secondary efficacy endpoints: Secondary efficacy endpoints for all study subjects will be determined both at baseline and at the end of treatment. They consist of the following:

- Vaginal pH
- Dyspareunia and vaginal dryness scores on the BSSC-W and the FSFI,
- Quality of life using the QOL-CSV.

IRB 239531 Sponsor: UAMS Version 15 0/7/07/2023 Page 18 of 22

Analysis Plan

Descriptive Analysis: Each efficacy endpoint will be summarized by treatment group and time point as the mean, standard deviation (SD), minimum, 1st quartile, median, 3rd quartile, and maximum. Within each subject, the endpoint's response to treatment will be defined (and calculated) as the endpoint's value at 12 weeks minus its value at baseline; the resulting endpoint responses will be summarized by treatment group as the mean, SD, minimum, 1st quartile, median, 3rd quartile, and maximum. Graphical displays will consist of box plots and scatter plots along with profile plots, a.k.a. "spaghetti plots", that show how the individual subjects respond over time to their assigned treatment. Adherence to distributional assumptions will be assessed, and data transformation to increase such adherence will be implemented, if warranted.

Primary Efficacy Analyses: To determine each treatment arm's VMI response to treatment, the Intrarosa® arm will be compared to the ReplensTM arm for the difference in their VMI responses using Student's t-test if group variances are equal, Welch's t-test if group variances are unequal, or Wilcoxon's rank-sum test if data violate normality assumptions. In keeping with the research hypothesis that the Intrarosa® arm will exhibit greater improvement in the VMI when compared to the ReplensTM arm after 12 weeks (± 1 week) of treatment, this primary-efficacy comparison will be conducted using a one-sided test at an $\alpha = 0.05$ significance level to look specifically for increased VMI response in the Intrarosa® arm. The follow-up of this primary-efficacy comparison will be analyzed using an ANCOVA model that has 12-week VMI as the outcome variable, treatment arm as the factor of interest, and baseline VMI as the continuous covariate.

Secondary Efficacy Analyses: For each secondary endpoint, the treatment arms will be compared for a difference in the endpoint at baseline, a difference in the endpoint at 12 weeks (± 1 week), and a difference in the endpoint's response to treatment. All comparisons will be conducted using 1-sided tests that employ a multiple-comparison-adjusted $\alpha = 0.01$ significance level to look specifically for improvements with Intrarosa® compared to Replens™. The tests will consist of Student's t-test, Welch's t-test, or Wilcoxon's rank-sum test depending on the endpoint's adherence to distributional assumptions. In follow-up analysis, each secondary endpoint will be analyzed using an ANCOVA model that has the endpoint's 12-week value as the outcome, treatment arm as the factor of interest, and endpoint's baseline value as the continuous covariate.

Sample Size and Power: The study is powered to detect an effect size of 0.8 SDs for the expected improvement in VMI response among subjects on the Intrarosa® arm compared to subjects on the ReplensTM arm. Specifically, if the study meets its enrollment goal of 60 subjects (30 in each treatment arm), then 30 subjects per arm provide Student's t-test and Wilcoxon's rank-sum test (both 1-sided at $\alpha = 0.05$) with 92.2% power and 91.2% power, respectively, to detect an effect size of 0.8 SDs in VMI response. Moreover, even if the study were to suffer an attrition rate of 20%, then the remaining 24 subjects per arm (48 subjects that remain) still provide Student's t-test and Wilcoxon's rank-sum test (both 1-sided at $\alpha = 0.05$) with 86.1% power and 84.9% power, respectively, to detect an effect size of 0.8 SDs in VMI response.

To see that a 0.8-SD effect size is reasonable for VMI response, we call attention to the studies of Archer *et al.* [14] and Labrie *et al.* [8]. Although neither study utilized VMI itself as the outcome, both studies utilized the percentages of P and S cells as outcomes when reporting the 12-week differences they observed between their DHEA (6.5mg) arms and their placebo arms. Archer *et al.* [14] observed treatment-arm differences of 1.52 SDs in %P cells and 1.02 SDs in %S cells at 12 weeks, whereas Labrie *et al.* [8] observed treatment-arm differences of 1.11 SDs in %P cells and 0.99 SDs in %S cells at 12 weeks. These prior observations of \geq 1-SD effect sizes for VMI-related endpoints show that it is reasonable to expect an effect size of 0.8 SDs for VMI response,

IRB 239531 Sponsor: UAMS Version 15 0/7/07/2023 Page 19 of 22

and thus that our study has sufficient power to achieve its research objectives.

Ethical Considerations

This study will be conducted in accordance with all applicable government regulations and University of Arkansas for Medical Sciences research policies and procedures. This protocol and any amendments will be submitted and approved by the UAMS Institutional Review Board (IRB) to conduct the study.

A Partial HIPAA Waiver for Recruitment will permit study staff to prescreen potential subjects prior to obtaining consent/HIPAA authorization to determine use of prohibited medical products requiring either an 8-week or 6-month washout in order to meet eligibility.

The formal consent of each subject will be obtained at UAMS before that subject is submitted to any study procedure using an IRB-approved consent form, which will describe this study and provide sufficient information in language suitable for subjects to make an informed decision about their participation in this study. The person obtaining consent will thoroughly explain each element of the document and outline the risks and benefits, alternate treatment(s), and requirements of the study. The consent process will take place in a quiet and private room, and subjects may take as much time as needed to make a decision about their participation. Participation privacy will be maintained and questions regarding participation will be answered. No coercion or undue influence will be used in the consent process. This consent form will be signed by the subject or legally authorized representative, and the individual obtaining the consent. A copy of the signed consent will be given to the subject, and the informed consent process will be documented in each subject's research record.

Dissemination of Data

Results of this study may be used for presentations, posters, or publications. The publications will not contain any identifiable information that could be linked to a subject. The study will be listed on clinicaltrials.gov in accordance with FDA requirements.

References

- 1. Kidwell, Kelley M., et al. "Patient-Reported Symptoms and Discontinuation of Adjuvant Aromatase Inhibitor Therapy." Cancer, vol. 120, no. 16, 2014, pp. 2403–2411, doi:10.1002/cncr.28756.
- 2. Baumgart, Juliane, et al. "Sexual Dysfunction in Women on Adjuvant Endocrine Therapy after Breast Cancer." Menopause: The Journal of The North American Menopause Society, 2012, p. 1, doi:10.1097/gme.0b013e31826560da.
- 3. Sinha, A., and A. A. A. Ewies. "Non-Hormonal Topical Treatment of Vulvovaginal Atrophy: an upto-Date Overview." Climacteric, vol. 16, no. 3, 2013, pp. 305–312,
- 4. doi:10.3109/13697137.2012.756466.
- 5. Chollet, Janet A. "Efficacy and Safety of Ultra-Low-Dose Vagifem (10 Mcg)." Patient Preference and Adherence, 2011, p. 571, doi:10.2147/ppa.s22940.
- 6. Basson R. Pharmacotherapy for women's sexual dysfunction. Expert Opin Pharmacother. 2009 Jul;10(10):1631-48. doi: 10.1517/14656560903004184.

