Potential research subjects have the ability to review the informed consent and DHEA flyer through MyChart prior to any clinic visit. The flyer provides a description of the program and its processes in layman's terms. These items are intended to augment the consenting process and provide a useful tool for the consenter and consentee to communicate. The potential subject will also have the option within MyChart to indicate whether they are interested in consenting to the study prior to their visit. The Arkansas Clinical Data Repository (AR-CDR) will be utilized to find and recruit subjects who may meet eligibility criteria. Information requested from AR-CDR will be a list of female patients between the ages of 18 and 70 years old with a history of breast cancer who are currently on an aromatase inhibitor and have been for at least 6 months. Patients who fit these criteria will be contacted via email, phone, or patient portal and asked if they are interested in learning more about the study. If they are, a study staff member may contact the patient via email, phone or patient portal to discuss further. If a patient prefers to not be contacted, they can opt out of further communications by responding via email, phone or patient portal to notify the research team.

Females of childbearing age and potential must have negative pregnancy test at screening. Subjects who are post-menopausal (as defined in the inclusion criteria) will not require a

IRB 239531 Sponsor: UAMS Version 15 0/7/07/2023 Page 8 of 22

pregnancy test.

At baseline, subjects will undergo a physical exam including clinical breast and gynecological exam. During gynecologic exams, the vaginal pH will be determined and a swab of vaginal epithelium will be sent to pathology to calculate the VMI. These will be used as objective physiologic markers to determine the improvement in vaginal atrophy. The cytologists reading the specimens will be blinded. If the VMI results are "unsatisfactory", the swab of vaginal epithelium will need to be recollected within 4 weeks of Day 1, Week 1 to calculate a new VMI.

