Appendix A: Study Calendar

	Pre- Study/Baseline ^a	Day1, Week 1 ^b	Week 2-12	End of Treatment ^c
Determine eligibility for study:	Χ			
Study consent discussed and signed	Χ			
Pregnancy test ^d	Χ			
Collect relevant disease-related data (mammogram, Pap				
smear)e, FSH levelf, baseline conditions, height, weight, and	X			
medical history				
Complete BSSC-W	Χg			Χg
Complete FSFI ^h	Χg			Χg
Complete DHEA Trial Clinical Supplemental Survey	Χg			
Physical exam (including gynecologic ⁱ and breast exams)	Χ			\mathbf{x}^{j}
Vaginal pH to be determined	Χ			X
Swab of vaginal epithelium collected and sent to pathology to calculate VMI ^k	X			х
Estradiol level ^l	Х			Х
Complete QOL-CSV	Χg			χg
Randomize to treatment arm	Χ			
Assigned treatment and study diaries dispensed to subject		Х		
Self-administration (starts same day as dispensed)				
Intrarosa® 6.5 mg insert nightly				
~OR~		x	x	
 Replens[™] 6.7 g prefilled applicator intravaginal two non- consecutive nights weekly 				
Collect AEs ^m		Х	Х	Х
Diary Submissions			Xn	Χo
Drug boxes and unused products collected from subject				Х
Follow up call			x ^p , ^q	

a Pre-study/Baseline should be completed within 28 days prior to Day 1, Week 1.

b Day 1, Week 1 visit may be done the same day as Pre-Study/Baseline visit if all Pre-Study/Baseline activities are completed and eligibility has been confirmed prior to Day 1, Week 1 activities.

c End of Treatment should be completed at week 12 from Day 1, Week 1, i.e., Week 12 ±1 week).

d Subjects who are post-menopausal will not require a pregnancy test. SoC pregnancy test results may be used if completed within 7 days of Day 1, Week 1.

e Mammogram (if deemed appropriate by the treating physician) and normal Pap must be documented within 12 months prior to study entry. If these are not documented in the medical history, they will be obtained for the study. SoC Pap and mammogram (if appropriate) may be used if completed within 28 days of Day 1, Week 1. Pap is not required for females whose cervix has been removed by surgery for reasons not related to cervical cancer or serious cervical pre-cancer.

f If FSH level is not documented in the medical history, one will be obtained prior to study entry.

g Should be completed in-person but can be completed over the phone, if necessary.

h FSFI is to be completed only if participant answers no to question 1 on the coinciding BSSC-W.

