i Gynecologic exam, including vaginal pH and VMI activities can take place on the same day as consent and Day 1, Week 1 as long they are completed after consent, all other eligibility criteria have been met, and prior to Day 1, Week 1 activities. SoC breast and pelvic exams may be used if completed within 28 days of Day 1, Week 1.

j During the gynecologic exam, a Pap smear may be performed at the treating physician's discretion if abnormal cervical changes are suspected.

k If the VMI results are "unsatisfactory", the swab of vaginal epithelium will need to be recollected within 4 weeks of Day 1, Week 1 to calculate a new VMI.

A report will be sent to FDA for any subject with an estradiol level out of the normal postmenopausal range at week 12 (±1 week).

m All AEs reported during clinic visits, on diaries, by phone or email, etc. are to be documented, assessed by the PI or designee, and tabulated.

n Diary progress should be submitted after Week 4 (±1 week), Week 8 (±1 week) of treatment. Diaries can be submitted in person, via self-addressed envelope to CTO, text photos to the research nurse cellphone, email photos to the research nurse email, sent photos through MyChart, or faxed to CTO. There will be no deviation for subjects who do not submit diary progress at Week 4 or Week 8.

o Diary progress should be submitted after Week 12 (±1 week) of treatment, or end of treatment. Diaries can be submitted in person, via self-addressed envelope to CTO, text photos to the research nurse cellphone, email photos to the research nurse email, sent photos through MyChart, or faxed to CTO. There will be a deviation for subjects who do not submit diary progress at Week 12 or if they come off treatment early.

Follow-up call should occur at 1 week ±3 days after Day 1, Week 1.

q Follow-up call should occur at 6 weeks ±1 week after Day 1, Week 1.

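### The repeat-swab rule for an unsatisfactory baseline VMI does not say before or after Day 1, so a same-day starter's repeat baseline could fall on treatment

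*Combined protocol and SAP*

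**What the plan says.** All references are to the combined protocol and SAP.

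- **Repeat rule.** The baseline paragraph of Study Design and Procedures says that after an unsatisfactory VMI result "the swab of vaginal epithelium will need to be recollected within 4 weeks of Day 1, Week 1 to calculate a new VMI". Appendix A, footnote k, repeats the rule in the same words. Neither place gives a direction in time.
- **Baseline window.** Footnote a: "Pre-study/Baseline should be completed within 28 days prior to Day 1, Week 1".
- **Timing of the VMI swab.** Footnote i allows it on the same day as consent and Day 1, "as long they are completed after consent, all other eligibility criteria have been met, and prior to Day 1, Week 1 activities".
- **Same-day start.** Footnote b: "Day 1, Week 1 visit may be done the same day as Pre-Study/Baseline visit if all Pre-Study/Baseline activities are completed" and eligibility is confirmed.
- **The calendar activity itself.** The row reads "Swab of vaginal epithelium collected and sent to pathology to calculate VMI". It is marked at both Pre-Study/Baseline and End of Treatment, and it carries footnote k.
- **Start of dosing.** The calendar has self-administration begin on the day the product is dispensed, which is Day 1.
- **Use of the value.** Under Efficacy Endpoints, VMI Response is the change from baseline to end of treatment. Under Primary Efficacy Analyses, baseline VMI is also the covariate in the follow-up ANCOVA.

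**The concern.** The listed baseline activity is complete once the swab has been collected and sent. A satisfactory result is not among the eligibility criteria, and neither the Randomization section nor the calendar makes allocation or dosing wait for cytology. A subject who has baseline and Day 1 on one day may therefore have taken a first dose before anyone knows the smear cannot be read. A pre-dose repeat is then no longer possible. A repeat in the following four weeks fits the literal rule, and the protocol gives no other instruction for that subject.

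VMI Response is a difference between two single swabs. If the first is taken after some weeks of active treatment, part of any drug effect is already in the value that is subtracted. The change score shrinks, mainly in the Intrarosa arm. The ANCOVA does not repair this, because its baseline covariate would then be a value that treatment can alter. The efficacy population asks for a baseline assessment but does not say that it must precede dosing, so nothing later in the plan removes such a value.

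**Working it through.** **1. Which way does the rule point?**

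| Provision | Bearing on a repeat baseline swab |
|---|---|
| Repeat rule (body text, footnote k) | Four-week limit around Day 1, no direction |
| Footnote a | Baseline lies in the 28 days before Day 1 |
| Footnote i | VMI swab precedes Day 1 activities |
| Footnotes d, e, i | Similar wording used for pre-treatment items |
| Footnote b | Baseline and Day 1 may coincide |
| Calendar, dosing row | First dose on the day of dispensing |
| Eligibility, Randomization | No satisfactory VMI required |

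The first group of footnotes suggests that a pre-dose swab is intended. The last three rows describe a sequence in which that intent cannot be met once a late unsatisfactory report arrives. The provisions conflict for that subject. Read as running after Day 1, the window reaches 28/84 = 33% of the way through treatment.

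**2. The plan's own power figures.** Inputs from Sample Size and Power: effect d = 0.8 SD, one-sided α = 0.05, n = 30 or 24 per arm. Student's t-test: df = 2n − 2, noncentrality δ = d√(n/2), power = P(noncentral t > t₀.₉₅,df).

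- n = 30: df = 58, critical value 1.672, δ = 0.8 × √15 = 3.098, power 92.2% (stated 92.2%).
- n = 24: df = 46, critical value 1.679, δ = 0.8 × √12 = 2.771, power 86.1% (stated 86.1%).

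Both reproduce.

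**3. Illustration of an on-treatment baseline.** Let f be the share of Intrarosa subjects whose baseline is taken on treatment, and s the share of the 12-week effect present at that swab. Both are assumptions; the documents give neither. With the SD and the Replens response unchanged, the expected difference is 0.8 × (1 − f × s).

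| f | s | Difference (SD) | Power, 30 per arm | Power, 24 per arm |
|---|---|---|---|---|
| 0 | – | 0.80 | 92.2% | 86.1% |
| 5% | 50% | 0.78 | 91.0% | 84.5% |
| 10% | 50% | 0.76 | 89.7% | 82.9% |
| 20% | 50% | 0.72 | 86.7% | 79.2% |

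For the third row: 0.8 × (1 − 0.10 × 0.50) = 0.76, and δ = 0.76 × √15 = 2.943 at 30 per arm.

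**4. The End-of-Treatment swab.** Week 12 ± 1 week is days 77 to 91. A window that closes on day 28 ends 77 − 28 = 49 to 91 − 28 = 63 days earlier. Footnote k therefore cannot serve that visit, although it sits on a row marked there. The Week-12 text gives no repeat rule of its own.

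**The case against.** The best answer is that the intent is clear. The calendar uses similar wording for other pre-treatment items: the pregnancy test (footnote d), standard-of-care Pap and mammogram (e), and standard-of-care breast and pelvic exams (i). Post-dose timing is worded differently, counted from or after Day 1. Four weeks equals the 28 days of footnote a, and footnotes b and i make same-day start conditional on baseline activities coming first. On this view only the words prior to are missing.

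Much of that stands. A reader might infer that the plan expressly permits an on-treatment baseline; footnotes a and i do not support that. Nor do the documents show that an unsatisfactory report can only arrive after dosing, since cytology turnaround is not given. What remains is that intent does not help once a first dose has preceded the report: the conditions in b and i are met when the swab is taken, not when it is found readable.

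A reader might also infer that an unsatisfactory Week-12 swab is lost. That does not follow. The body-text rule belongs to the baseline paragraph, other row footnotes in the calendar govern one visit only, and nothing bars a repeat inside Week 12 ± 1 week. The gap there is an unstated procedure.

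Finally, larger power losses can be produced. With f = 20% and s = 100% the difference is 0.64 SD, and power is 79.0% at 30 per arm or 70.5% at 24. Nothing in the documents supports that many affected subjects, or the full 12-week effect within four weeks.

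**Conclusion.** The concern holds as an unresolved inconsistency with a route to bias in the primary endpoint. It requires three things together: an unsatisfactory baseline smear, a first dose taken before the report, and a repeat taken on treatment. Where they coincide, VMI Response is likely to be understated, mainly in the Intrarosa arm, so the bias runs against Intrarosa and is not a route to a false positive.

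Its size cannot be derived, because the documents give no unsatisfactory rate, no cytology turnaround and no four-week VMI effect. The fall from 92.2% to about 89.7% is an illustration under f = 10% and s = 50%. The stated power and sample size are correct as they stand. The point merits action because a missed pre-treatment value cannot be recovered later and prevention is cheap.

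**What to change.** Amend the baseline paragraph of Study Design and Procedures and footnotes b, i and k of Appendix A to state that:

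1. a satisfactory baseline VMI must be reported before randomisation and first dose;
2. any repeat baseline swab falls within the 28 days before Day 1;
3. a VMI taken after the first dose is not used as baseline, either in VMI Response or in the ANCOVA.

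As a secondary clarification, state that footnote k applies to baseline only, and that an unsatisfactory End-of-Treatment swab may be repeated within the Week 12 ± 1 week window.

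The cost is a short amendment, and some subjects lose same-day start while the cytology report is awaited. The sample size stays at 60, and planned power stays at 92.2% (86.1% at 24 per arm).
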